## **Adverse Events (AEs) and Serious Adverse Events (SAEs) Related to the EDORA Trial**

### ***a) Cardiac Ablation***

Cardiac ablation is standard of care. Patients who have attempted to control their arrhythmia via AADs with no positive outcome and/or have suffered serious side effects from certain medications are advised to undergo this procedure. Most symptoms or side effects related to cardiac ablation are not from the procedure itself. Patients may complain of back ache from lying on the operation table for a longer time. Sore throat is a common side effect of the procedure due to the anesthetic use during intubation and some arrhythmia may be experienced afterwards (blanking period).

Direct effects of cardiac ablation include bleeding or infection at the site where the catheter was inserted, puncturing of the heart, damage to heart valves, damage to the heart's electrical system, which could worsen the arrhythmia and require a pacemaker to correct. In addition, venous thromboembolism, pulmonary vein stenosis, stroke or heart attack could occur. Renal damage from contrasting dye used during the procedure, and even death may occur in rare cases.

### ***b) Dronedarone***

Antiarrhythmic drugs such as, dronedarone can be prescribed as standard of care. They too carry adverse effects which include; pulmonary events (cough, dyspnea, pulmonary toxicity), thyroid toxicity (hypo- or hyperthyroidism), hepatic toxicity, bradycardia <50bpm, QT-interval prolongation, gastrointestinal events (loss of appetite, nausea, vomiting, abdominal pain and diarrhea), neurological events (dizziness, headache, asthenia, peripheral neuropathy), chest pain or discomfort, heart failure, decompensation in patients with heart failure, and an increase in serum creatinine.

Although a black box warning has been issued by the FDA, dronedarone's associated risk of death and stroke is based on patients with heart failure, decompensated heart failure, or permanent atrial fibrillation. These classes of patients fall into the exclusion criteria and thus, will not be enrolled in this trial. Dronedarone is also contraindicated in AF patients who cannot be cardioverted into normal sinus rhythm.

### ***c) CMR Scan***

There will be approximately 3 CMR scans throughout the trial period. The 1st CMR scan will be taken preferably within 90 days prior to ablation. Gadovist, Class II macrocyclic gadolinium, low risk, or a similar agent will be used as the contrasting agent to visualize the heart.

Discomfort in claustrophobic patients undergoing an MRI can happen in which case the image processing will be halted immediately.

## ***Risks Associated with Gadolinium Contrast in CMR***

Page 30 of 49

Version 4.0:  
Revision Date: April 27th, 2022

Copyright© April 2022 Tulane University School of Medicine, Academic Research Organization on behalf of the Principal Investigator.  
All rights reserved.

TULANE UNIVERSITY  
Academic Research Organization

Risks associated with gadolinium include:

- Discomfort, tingling, warmth of the lips, metallic taste in the mouth, nausea, or headaches. This risk is small (1 in 100 people) and in most instances these symptoms disappear very quickly.
- Type 1 hypersensitivity reaction. Clinical staff will stop its use immediately and will provide antihistamine medication or epinephrine, depending on the severity of the reaction. Severe reactions rarely occur, < 1 in 300,000 people.
- Approximately 4% of patients with severe kidney disease receiving gadolinium based contrasting agents are at a higher risk of developing Nephrogenic Systemic Fibrosis (NSF). Although rare, this disease can be serious, causing skin thickening (fibrosis) as well as thickening in other organs of the body such as, the brain, heart and bone and can even cause death. NSF has also been reported in those who have had recent major surgery, infection or have cancer.  
There have been no reports of NSF in patients receiving gadolinium who have normal kidney function. (Patients with acute or chronic severe kidney disease or with a low glomerular filtration rate (GFR), <30 mL per minute per 1.73 m^2 will be excluded from the EDORA trial).
- A pregnancy test will be conducted before each CMR scan as gadolinium may cause harm to the fetus. (Any pregnant patients at the time of enrollment will be excluded from the trial).

### *Unanticipated Problems*

These can be incidents, experiences or outcomes that are unexpected but related to participating in the EDORA trial. These suggest that the trial places patients at a greater risk of harm than was previously known or recognized.

#### **Categories that are considered UP:**

- Adverse Device effects (*BodyGuardian® MINI Plus EL-ECG monitoring device*)
- Consent Deviation
- Data and Safety Monitoring Reports that indicate that frequency or magnitude of harms or benefits may be different than initially presented to the IRB
- Change in FDA labeling or withdrawal from marketing of a drug and or device used in the EDORA trial
- Breach of Privacy and Confidentiality (*e.g. unauthorized use of disclosure of protected health information.*)
- Incarceration of a participant
- Warning or determination letters issued by any funding agency or regulatory body including Office of Human Research Protections (OHRP), Department of Health and Human Services (DHHS), Food and Drug Administration (FDA)

Any unanticipated problems should be reported within 24 hours and a completed report will be required within 3 working days of the event. Once received, this report will be sent immediately (within 24 hours) to the DSMB. In accordance with IRB requirements, the investigator will be required to notify Tulane University ARO, their local IRB as well as the IRB of record (WCG).

In an unlikely event that the medical monitor believes that the unanticipated problem warrants immediate suspension in the trial, and the DSMB cannot be reached, the Principal Investigator will be informed, and all investigators will be told to cease enrollment in the trial. Again, only with the approval of the DSMB will the trial resume enrollment.

If the DSMB is notified of any SAEs that were unexpected, study related or unanticipated problems, decisions will be made as to whether the trial will continue without changes made to the protocol. If the

trial undergoes suspension, the Principal Investigator will be notified, and all clinical investigators will be instructed to report this to their local IRB or ethics board.

The DSMB will review all adverse events during their scheduled meetings. Tulane University ARO will prepare a summary report of all AEs for these meetings.

### *Adverse Events & Reporting*

Adverse events do not necessarily require reporting to the IRB or Tulane University ARO (unless its frequency or intensity is greater than originally anticipated and are therefore deemed as serious). Local IRB requirements differ and therefore, the recommendation is for sites to follow their regulatory policies regarding this matter.

In accordance with IRB requirements, the investigator should notify Tulane University ARO, their local IRB as well as the IRB of record (WCG) of all SAEs within 24 hours.

A completed and comprehensive report will be required within 3 working days of the event. The medical monitor will assess all incoming SAE's that have been reported. The site investigator will need to sign all adverse event forms after full review.

All SAEs will be stored on DACIMA and will be readily available for review by DSMB members.

In an unlikely event that the medical monitor believes that an unexpected, but trial related SAE warrants an emergent cessation of enrollment in the trial, the DSMB Chair will be immediately consulted. If the board members concur with the medical monitors assessment, or the DSMB Chair cannot be reached, the Principal Investigator will be notified immediately, and all clinical investigators will be told to cease enrollment in the trial. Only with the approval of the DSMB will the trial resume.

### *Adverse Event (AE) Data Collection Procedures*

All AEs, including serious adverse events (SAEs), whether anticipated or unanticipated, will be recorded according to the date of when they first occurred, the severity, and their duration, as well as any treatment that was prescribed.

Any medical condition that was present at the time of randomization, recorded in the patient's baseline medical history which remains unchanged or improves, will not be recorded as an AE at subsequent evaluations. However, worsening of a medical condition that was present at the time of randomization will be considered a new AE and must be reported.

Any abnormal laboratory results at the time of randomization, recorded in the patient's baseline history which remains unchanged will not be recorded as an AE. However, abnormal laboratory results drawn during the trial that are clinically significant will be recorded as an AE and the clinical investigator will assess the severity and relationship it may have to the clinical trial.

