#### **9) Left Ventricle (LV) Structural and Functional Changes**

LV structure, or fibrosis (%), will be assessed using native T1 and ECV MRI sequences included in the CMR imaging. LV function will be measured as the ejection fraction (LVEF) and LV strain using cine-MRI sequences performed as part of the CMR protocol (see appendix)

Secondary endpoints will be analyzed at 3 (0-3) and 13-months (0-13) post-ablation and compared between the two trial arms.

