### *Blinding*

This is a single blinded clinical trial. Therefore, study participants will be unaware as to whether they are receiving drug or placebo. Site investigators cannot be blinded to the treatment administered since these site investigators may also be medically treating the study participant at the same time. Site investigators will need to be fully aware of the medications and associated dosages administered to their study participants to maximize study participant safety. To mitigate bias, independent ECG rhythm readers and CMR scan readers will not have access to the patient's treatment arm. In addition, all investigators, study monitors, medical monitors, data analysts, and the study team may have access to information related to the treatment arms when required.

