## **Baseline Visit**

### *Biological Samples*

Blood samples may be drawn at baseline and at the 3-month and 12-month visits. The timeframe for blood draw results will be based on institutional requirements and left at the discretion of the treating physician. In addition, blood samples to assess for the presence of biomarkers of fibrosis, inflammation, and cardiovascular disease will be recorded at these visits. These include NT pro-BNP, soluble ST2, and C-reactive protein and Galectin-3.

All blood samples will be processed at the trials' local sites, and the results will be entered onto the electronic database capture platform, DACIMA (Software Inc), after each visit. Blood samples will not be shipped or stored after processing.

List of Study Labs	
Panel:	Specific Tests:
Liver Panel	ALT, AST, ALP, and GGT
Renal Panel	Creatinine, BUN/Cr, GFR
Cholesterol Panel	Total cholesterol, HDL, LDL, and Triglycerides
Basic Panel	HbA1c, CBC, BMP
Coagulation Panel	PT/INR, PTT
Inflammation/Fibrosis/CVD Biomarkers	NT-ProBNP, Soluble ST2, C-RP, and Galectin-3

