### **Adverse Events (AEs) and Serious Adverse Events (SAEs)**

An adverse event (AE) is any unforeseen medical occurrence experienced by a patient in the clinical trial. This event can constitute a disease, related signs or symptoms to the investigational drug or study device. All clinical investigators will evaluate and record these events on the appropriate form. Arrhythmias will not require reporting as an AE because the patient will be transmitting ECGs via their ECG device, and these will be reviewed and interpreted by the central monitoring team. A serious adverse event (SAE) is an adverse event that results in death, hospitalization, is life threatening or requires intervention.

For each AE+/SAE, the clinical investigator will record whether an intervention was also required:

- **Intervention-** Surgery or procedure
- **Other treatment-** medication initiation/change, discontinuation
- **None-** no action was taken

In addition, the clinical investigator will also record any clinical outcome of each AE+/SAE:

- Death
- AE resolved or the symptoms/signs that constitute the AE returned to baseline
- AE resolved with permanent sequelae
- Symptoms that constituted the AE are ongoing

Each participating clinical trial site and its investigator has a primary responsibility for the safety of the patients under his or her care. In person visits will occur at 3 and 12-months, and follow-up phone calls/visits will be held at 6, 9-months and towards the end of the clinical trial (Month 13). Clinical investigators or the research team may schedule additional clinic visits according to their standard of

care or as needed to maintain patient safety during the trial. These visits as well as any new or worsening symptoms or events will also be recorded on DACIMA during this time.

All adverse events that occur after randomization will be evaluated throughout the follow-up periods and will be collected and stored on DACIMA.

Serious adverse events (SAE) must be reported in an expedited manner to the IRB and Tulane University ARO, to allow for optimal monitoring of patient safety and care.

Please refer to the Adverse Events & Reporting section for provided timelines on reporting AE, SAE and UP and completing the respective logs.

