### *Follow-up of SAEs, Unexpected Events, and Related Events*

Any SAEs that are unresolved at the time of the patient's termination from the trial will be followed by the clinical investigator until the events have been resolved, the patient is lost to follow-up, or the adverse event is otherwise explained or has stabilized.

For the safety and adverse events monitoring data, incidents of adverse events will be summarized by event type, grade, and body system. The proportion of patients with AEs will be calculated and presented with a 95% confidence interval.

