#### **D. Analysis of the secondary endpoints**

The secondary endpoints will be analyzed only as supporting evidence. There will be no intention to claim treatment benefits for the listed secondary endpoints. As such, data analysis for secondary endpoints are purely for descriptive purposes and not for drawing inferences.

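### No on-treatment, by-arm summary of the scheduled liver and renal values is planned, so non-serious, asymptomatic abnormalities reach the safety comparison mainly through an undefined judgement, most plausibly by unblinded investigators

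*Combined protocol and SAP*

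**What the plan says.** The protocol's section on adverse events related to dronedarone lists hepatic toxicity and a rise in serum creatinine. Biological Samples lists a liver panel (ALT, AST, ALP, GGT) and a renal panel (creatinine, BUN/Cr, GFR), states that "Blood samples may be drawn at baseline and at the 3-month and 12-month visits", and has the results entered in DACIMA after each visit.

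Adverse Event (AE) Data Collection Procedures sets the rule for laboratory findings: "abnormal laboratory results drawn during the trial that are clinically significant will be recorded as an AE". It gives no multiple of normal, no absolute value and no grading scale. It assigns severity and relationship to the clinical investigator, but does not say who decides on clinical significance. The general AE section says that "All clinical investigators will evaluate and record these events on the appropriate form", and Adverse Events & Reporting says that "The site investigator will need to sign all adverse event forms after full review". Under Blinding, "Site investigators cannot be blinded to the treatment administered"; the ECG and CMR readers are the assessors kept from the allocation.

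The stated safety analysis is that "incidents of adverse events will be summarized by event type, grade, and body system", with the proportion of patients having AEs and a 95% confidence interval. Participant safety is a secondary endpoint. For these, "Secondary endpoints will be analyzed at 3 (0-3) and 13-months (0-13) post-ablation and compared between the two trial arms", and section D of the statistical methods calls the analysis "purely for descriptive purposes and not for drawing inferences".

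**The concern.** The plan already collects objective values for two known drug effects, yet the only stated route by which an abnormal value reaches the between-arm comparison is a person's decision to call it an AE. If that person knows the arm, the decision can differ by arm. The label text in Appendix C gives reasons for either direction: the liver warning (5.5) could make an investigator readier to flag an enzyme rise on dronedarone, while the explanation of the small creatinine rise (5.9) could make the same investigator dismiss one.

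At stake is how well the laboratory AE lines describe dronedarone's effect. Nothing in either co-primary analysis depends on it.

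**Working it through.** The plan has no figure of its own to reproduce here. The check is mainly one of text.

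**1. Is an on-treatment laboratory summary stated anywhere?**
- Follow-up of SAEs, Unexpected Events, and Related Events covers AE incidence only.
- Statistical methods, section B, compares baseline clinical measurements. Baseline laboratory values could fall under this, but it is a check on randomization.
- Sections C and D name no laboratory value.
- Database Lock describes data verification before analysis.
- Unanticipated Problems has the coordinating centre prepare an AE summary for the DSMB.

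So no section states one for on-treatment values.

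**2. Which abnormalities depend on the judgement?** Symptoms or disease make an event an AE under the general definition. A worsened pre-existing condition is an AE by rule. Serious events go to the medical monitor and are available to the DSMB. What remains is the non-serious, asymptomatic abnormal value.

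**3. Who judges?** This is an inference. The investigator evaluates and records AEs, rates severity and relationship, and signs the form. No other assessor is named for laboratory results.

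**4. How large might the bias be? (Illustration only.)** The documents give no abnormality rate or flagging probability, so both are assumed. Patients tested per arm are taken as 165 × 0.8 = 132, borrowing the 20% loss assumed for recurrence, which is not a laboratory completion rate.
- Spurious difference = true rate × difference in flagging probability.
- Sampling half-width = 1.96 × √(2p(1−p)/132).

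| True rate in both arms | Mild values, flagging 0.9 v 0.5 | Marked values, flagging 1.0 v 0.9 | Sampling half-width |
|---|---|---|---|
| 2% | 0.8 points | 0.2 points | 3.4 points |
| 6% | 2.4 points | 0.6 points | 5.7 points |
| 10% | 4.0 points | 1.0 points | 7.2 points |

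The relative risk is multiplied by 0.5/0.9 = 0.56 to 0.9/0.5 = 1.80 for mild values, and by 0.9/1.0 = 0.90 to 1.0/0.9 = 1.11 for marked values. In every row the bias is smaller than the sampling error.

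**5. What should the summary lead with?** Appendix C (5.9) gives a creatinine rise of about 0.1 mg/dL. At an assumed baseline of 1.0 mg/dL that is 10%, and a cut-off of 1.5 times baseline needs 50%, so a count above that cut-off would not show the shift. A difference in mean change has 95% half-width 1.96 × SD × √(2/132). For an assumed SD of change of 0.15 to 0.30 mg/dL this is 0.036 to 0.072 mg/dL, so a 0.1 shift could be seen. Change from baseline should come first.

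**6. Why scheduled values only?** Physicians who know the arm may order extra tests. Assume each test has the same independent 2% chance of crossing a cut-off. Two tests give 1 − 0.98² = 4.0% ever crossing and four give 1 − 0.98⁴ = 7.8%. Two extra tests in one arm thus create 3.8 points with no true difference (2.0 points at 1% per test, 5.6 at 3%).

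**The case against.** The strongest reply is that little is at risk. Safety is secondary and descriptive, serious and symptomatic injury has its own routes, and the raw values sit in the database, so a table can be made at reporting. The illustrated bias rests wholly on assumed inputs and stays below sampling error. Investigator judgement is also not always error: treating a 0.1 mg/dL creatinine rise as unimportant agrees with the label.

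Most of this stands, and it sets the modest level of the point. It does not remove the point. Bias does not shrink as patients are added. Blinding also allows data analysts access to the arms when required, so cut-offs and windows chosen at reporting could be chosen with allocation known. Prespecifying them costs little.

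A reader might infer more than the text supports:
- *That the laboratory values are used nowhere.* Baseline values may enter the section B comparison, and the DSMB reviews safety data under a charter that may include laboratory tables.
- *That the blood draws are optional.* The permissive wording in Biological Samples is largely answered by the 3-Month Visit and 12-Month Visit sections, which say sites will collect blood for labs.
- *That there will be no month-12 liver or renal values.* The month-12 list in Study Schedule names only fibrosis and inflammation biomarkers. However, Biological Samples lists the panels with a 12-month draw, the 12-Month Visit section equates that visit with month 3, and the Schedule of Events marks a blood draw.

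**Conclusion.** The point holds as a limited gap. The protocol states no on-treatment, by-arm summary of the scheduled liver and renal values. For non-serious, asymptomatic abnormalities, the descriptive safety comparison therefore rests mainly on an undefined judgement, most plausibly made with knowledge of the arm. That the site investigator makes this decision is inferred from the AE recording and signing duties.

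The size and direction of any bias are unknown; the figures above only show what assumed inputs would give. It would bear on the laboratory AE lines, with less effect on the overall proportion of patients with any AE. The documents do not support a conclusion that liver or renal harm would go unnoticed or that the trial's main results are compromised. The month-12 omission is a small inconsistency between sections. The change is a cheap improvement, worth making.

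**What to change.** Add to the safety analysis in Follow-up of SAEs, Unexpected Events, and Related Events a prespecified descriptive summary by arm:
- Use the scheduled month-3 and month-12 draws only, one value per patient and visit: the one nearest day 90 or day 365 within the 30-day window.
- Lead with change from baseline for ALT, AST, ALP and creatinine, marking whether the patient was on study drug at the draw.
- Give the number tested, and the number and percentage beyond cut-offs that the sponsor fixes in advance. Examples are ALT or AST above 3 times the site's upper limit of normal and creatinine at least 1.5 times baseline. These serve reporting and are not rules for care.
- Show the investigator-judged AEs beside it, and list unscheduled values separately.

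As a minor consistency correction, name creatinine and the hepatic panel in the month-12 list of Study Schedule.

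The cost is analysis wording, one or two tables and a short protocol edit. Because samples are processed locally, site reference ranges must be held in DACIMA. Two post-baseline draws miss abnormalities between visits: the nominal gap is 365 − 90 = 275 days, and only the month-3 draw falls in the first 6 months that the liver warning singles out. Patients off drug at month 12 would dilute any difference, and missing draws may differ by arm, which is why the number tested should be shown.
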